5.5 Subject Compliance Monitoring

All drug accountability records must be kept current. The investigator must be able to account for all opened and unopened study drug. These records should contain the dates, quantity, and study medication: dispensed to each patient, returned from each patient (if applicable), and disposed of at the site or returned to the sponsor or designee. All accountability records must be made available for inspection by the sponsor and regulatory agency inspectors; photocopies must be provided to the sponsor at the conclusion of the study. All drug compliance records must be kept current and must be made available for inspection by the sponsor and regulatory agency inspectors. Patients will complete a dosing diary to document compliance with self-injection of study drug.

Any subject who is significantly non-compliant with the study drug regimen may be withdrawn from the study.

5.6 Prior and Concomitant Therapy

Treatment with live (attenuated) vaccines, investigational drugs (other than dupilumab), or selective opioid antagonists are prohibited for patients actively enrolled onstudy.

Treatment with concomitant medications for chronic hepatic pruritus except for selective opioid antagonists is permitted during the study. This includes basic skin care (cleansing and bathing), emollients, topical anesthetics, and antihistamines for any duration. Medications used to treat chronic disease such as diabetes, hypertension, and asthma are also permitted; if there is any question regarding whether a concomitant medication may be used during the study, the study site should contact the medical monitor.

Page 15 of 29

[name]

[name]

[name], DO

CONFIDENTIAL

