3.6 Primary Safety Endpoints

This is an exploratory efficacy study with no specific primary safety endpoint. Adverse events will be tracked and reported using Good Clinical Practice standards and as described in Section 8 of this protocol.

Page 10 of 29

[name]

[name]

[name], DO

CONFIDENTIAL

The safety of dupilumab in this population will be assessed by evaluating the detailed medical history through physical examination, vital signs, and clinical laboratory testing. Concomitant medications and procedures will be collected from time of informed consent to the end of the study.

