3.7 Identification of Source Data

The following source data will be directly recorded on the Case Report Form (CRF):

- Screening and documentation of adverse events
- Confirmation of patient counseling and education
- PNRS score
- VRS score
- 5D Pruritus Score
- CLDQ questionnaire

The following source data will not be directly recorded in the CRF, but will be captured in supportive documentation to include study source documents and the EMR:

- Laboratory results and clinical interpretation of the values

4 Subject Selection Enrollment and Withdrawal

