4.2 Exclusion Criteria

Subjects who meet one or more of the following criteria will not be considered eligible to participate in the clinical study:

1. Male and/or female subjects under 18 years of age.
2. Pruritus due to a primary inflammatory skin dermatosis or other forms of psychogenic pruritus utilizing skin biopsies as needed.
3. Pregnant females

4. History of intrahepatic cholestasis of pregnancy
5. Any form of chronic hepatic pruritus associated with underlying malignancy
6. Liver transplant recipients
7. Allergy to dupilumab or its ingredients
8. Inability to provide informed consent
9. Concomitant use of selective opioid antagonists
10. Subjects with severe asthma (requiring high-dose inhaled or systemic corticosteroids)
will be excluded from the study.
11. Patients with known helminth infections

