4.4 Early Withdrawal of Subjects

4.4.1 When and How to Withdraw Subjects

Patients are free to withdraw at any time and for whatever reason. No data will be collected for withdrawn subjects. Withdrawn subjects may be replaced within the accrual period. There will be no follow-up for withdrawn subjects. Pre-specified reasons for discontinuing include, but are not limited to, the following:

- Patient Request: Patient decided that he/she did not want to continue (for any reason)
- Sponsor/Principal Investigator Request: Patients may be withdrawn from the study for any reason, at the discretion of the Sponsor/PI.
- Adverse Event: Patient experienced a related or unrelated event that would interfere with the study objectives/evaluation
- Lost to Follow-up: Patient did not come in for a visit and could not be reached by phone
- Treatment Failure: If in the Principal Investigator and/or Investigators' judgment, the patient's condition required another form of treatment
- Inclusion/Exclusion Discrepancy/Violation: Patient should not have been enrolled
- Noncompliance: Patient is not complying with the protocol requirements (i.e. visit schedule, dosing, regimen, etc.); a patient is to be withdrawn if he/she misses two consecutive visits
- Other: Any other reason

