6.3 Visit 3 (Week 6± 5 days)

The following information will be collected:

1. Inventory of existing medications and procedures

2. Adverse events

The following procedures and assessments will be conducted:

1. PNRS score; collect pruritus scoring journal
2. VRS score
3. Vital signs including; height, weight, body temperature, blood pressure, pulse rate
4. Physical examination
5. Laboratory samples including; CBC with differential, AST, ALT, INR
6. Dispense pruritus scoring journal; review instructions

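### Changes in other itch treatments during the study never enter the analysis, so improvement after an added treatment counts as dupilumab response

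*Combined protocol and SAP*

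**What the plan says.** **What is allowed.** Section 5.6 states: "Treatment with concomitant medications for chronic hepatic pruritus except for selective opioid antagonists is permitted during the study". Its examples include "topical anesthetics, and antihistamines for any duration". It also bars live vaccines and other investigational drugs, and for doubtful medications it says "the study site should contact the medical monitor". The only itch treatment named as an exclusion in 4.2 is "Concomitant use of selective opioid antagonists". Neither 4.1, 4.2 nor 5.6 requires background itch treatment to be stable before or during the study.

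**What is recorded.** Section 3.6, on safety, states: "Concomitant medications and procedures will be collected from time of informed consent to the end of the study". Visits 2 to 6 each list "Inventory of existing medications and procedures". Medications are not among the items that 3.7 says go directly onto the CRF. The visit lists mention neither start dates nor doses, and the events table has no medication row.

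**What is analysed.** Section 7.2 averages daily PNRS scores over the pre-treatment week and over weeks 1–6, 7–12, 13–18 and 19–20. It summarises percent change, estimates the proportions improving by at least 3 and at least 4 points, and compares each period with pre-treatment by signed-rank test. Missing data are filled by last observation carried forward. Section 7.3 includes everyone who received study drug, and its one sensitivity analysis excludes subjects who withdrew. None of this refers to the medication records.

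**The nearest safeguard.** Section 4.4.1 lists Treatment Failure as a reason for discontinuing, where in the investigator's judgment the patient's "condition required another form of treatment".

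**The concern.** Section 1.1 names sedating antihistamines, bile salt binders, rifampin, serotonin reuptake inhibitors, phototherapy and plasma exchange as standard treatment for this symptom, and 5.6 bars none of them. A subject could add one, improve, stay on study and be counted as a dupilumab responder. No control arm would show how much improvement comes from such additions.

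Section 7.1 supports attribution by arguing that this pruritus persists and does not remit on its own. That argument concerns the natural course of the disease. It does not cover improvement after another itch treatment is added.

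At stake are the descriptive summaries on which 7.2 puts its focus, and which section 13 says could support a larger trial if favorable. With 12 subjects, one misattributed responder is 1/12 = 8.3 percentage points. The data needed to see this are largely planned for collection, but no planned output shows them.

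**Working it through.** The plan has no figure to reproduce: 7.1 reports no power analysis, effect size or SD. What follows illustrates the possible size.

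**Inputs from the documents:** n = 12 (3.2); responder thresholds of 3 and 4 points, the signed-rank test and the 0.05 level (7.2).

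**Assumed inputs:** no drug effect; individual improvements distributed N(0, SD 2), ignoring the bounds of the scale; k = 1, 2, 4 or 6 subjects add treatment, each gaining b points over the averaging period; a two-sided test, since 7.2 does not state sidedness.

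**Test rule.** For n = 12 the exact signed-rank test rejects when the smaller rank sum is at most 13, with two-sided size 0.0425. About 2.1% therefore falls on the improvement side when nothing is going on.

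**Who adds treatment matters.** Two extremes were simulated: the k subjects chosen at random, and the k subjects with the worst changes. For random choice the responder rate has a closed form:

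rate = [k·P(N(b,2) ≥ 3) + (12 − k)·P(N(0,2) ≥ 3)] / 12

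With b = 3 the two probabilities are 0.5 and 0.0668. For k = 2: (2 × 0.5 + 10 × 0.0668)/12 = 1.668/12 = 13.9%.

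Results for b = 3 over the whole period:

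| Subjects adding treatment | 3-point responders, random | 3-point responders, worst k | Significant improvement, random | Significant improvement, worst k |
|---|---|---|---|---|
| 0 | 6.7% | 6.7% | about 2% | about 2% |
| 1 | 10.3% | 6.7% | about 4% | about 8% |
| 2 | 13.9% | 6.7% | about 6% | about 21% |
| 4 | 21.1% | 7.5% | about 17% | about 59% |
| 6 | 28.3% | about 12% | about 39% | about 87% |

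The two outputs move in opposite directions. Adding 3 points to a subject who was getting worse seldom reaches the 3-point threshold, but it removes a large negative rank from the test.

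**Smaller or later benefit.** A 3-point treatment begun halfway through a six-week period shifts that period's mean by 3 × 21/42 = 1.5 points. Random assignment then gives responder rates of 8.0/9.3/12.0/14.7% for k = 1/2/4/6. With b = 1 they are 7.4/8.2/9.7/11.3%. If the worst subjects add treatment, the rate stays at 6.7–6.8% in both cases.

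**Mean change.** The mean shifts by k·b/12 whoever adds treatment. For k = 2 that is 2 × 1/12 = 0.17 to 2 × 3/12 = 0.5 points. Across baselines of 9 down to 5, this is 0.17/9 = 1.9% to 0.5/5 = 10% of percent change.

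**The case against.** **Treatment is more likely to be added by subjects who are not improving.** This is sound. In that case the responder rate barely moves for small k, so a reader should not infer that every subject who adds treatment contributes 8.3 points; that holds only if the added treatment carries the subject over the threshold. The same selection makes the signed-rank inflation larger, so a remedy limited to responder proportions would miss much of the problem.

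**The bias can run the other way.** Subjects may cut back antihistamines as itch improves, which would understate the drug effect. This stands.

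**The plan already has safeguards.** Treatment Failure in 4.4.1 may remove some of these subjects, with their last score carried forward. It is discretionary, is not tied to starting a treatment that 5.6 permits, and does nothing for subjects who stay on. Referral to the medical monitor decides whether a medication may be used, not how later scores are analysed.

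**The records exist, and this is an exploratory pilot.** A reader might infer that other treatments go unrecorded; 3.6 and the visit lists show otherwise. The omission from 3.7 is weak evidence, since that list covers only data written directly on the CRF. An as-observed analysis with background treatment permitted is also legitimate, and 1.1 says standard treatments often fail. These points lower the priority. They do not supply an output that shows the effect of added treatment.

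**Conclusion.** The point holds as a low-priority improvement. The documents set no condition on changes in permitted itch treatments, and the analysis never uses the records of them. In a single arm, improvement after an addition is therefore credited to dupilumab in the percent change, the signed-rank comparisons and the responder proportions.

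The size cannot be stated. The number adding treatment, the benefit and the SD are all assumptions, and the table's two columns for each output are extremes of selection, not estimates. A reader might infer that a favorable result would be explained by added treatment, or that 5.6 permits anything. The documents support neither: they give no rate of added treatment, and 5.6 does bar opioid antagonists and investigational drugs.

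**What to change.** Keep the as-observed analysis as the main one. Add to 7.2 a sensitivity analysis based on a list of itch treatments fixed before data review, drawn from those in 1.1 that 5.6 does not bar. State whether topical anesthetics, procedures and partial opioid antagonists are on the list.

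- **(a) Responder endpoints.** Count a subject who starts or increases a listed treatment after week 0 as a non-responder at 3 and 4 points, from the period containing that date onward.
- **(b) Percent change and signed-rank test.** Repeat both using only daily PNRS scores recorded before the addition, carrying the last such period mean forward under the plan's existing carry-forward rule.
- **(c) Listing.** For each subject, give all itch-treatment changes with dates, including reductions, beside percent change by period. Make sure start dates and dose changes are recorded.

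Separately, reconcile 5.6 with 4.4.1, so that it is clear how added itch treatment relates to withdrawal for Treatment Failure. No clinical rule is proposed here.

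The cost is a paragraph of SAP text, one derived flag, one listing and possibly one or two CRF fields. The rule in (a) is conservative. With a true 2-point effect and SD 2, P(N(2,2) ≥ 3) = 30.9%. If 2 of 12 subjects add a treatment that does nothing, the rate reads 30.9% × 10/12 = 25.7%; with 6 of 12 it reads 15.4%. In (b), carrying early scores forward can also miss a later drug effect. Both results therefore stand beside the as-observed ones and do not replace them.

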5.7 Packaging

Dupilumab injection is a clear to slightly opalescent, colorless to pale yellow solution, supplied in single-dose pre-filled syringes with needle shield. Each pre-filled syringe with needle shield is designed to deliver 300 mg of dupilumab in 2 mL solution. Dupilumab is available in cartons containing 2 pre-filled syringes with needle shield.

Pre-filled syringes will be shipped to the Mayo Clinic Research Pharmacy in Florida and then labeled upon receipt with statement "Caution: New Drug Limited by Federal law for investigational use."

5.8 Masking/Blinding of Study

This is an open-label pilot investigation. Masking and blinding procedures are not applicable. Qualitative and quantitative evaluations of response to treatment will be recorded.

5.9 Receiving, Storage, Dispensing and Return

5.9.1 Receipt of Drug Supplies

The drug will be shipped by Regeneron Pharmaceuticals to the Mayo Clinic Research Pharmacy in Florida. Upon receipt, an inventory will be performed and a drug receipt log filled out by the person accepting the shipment. Designated study staff will count and verify that the shipment contains all the items noted in the shipping invoice. Any discrepancies, damaged or unusable study drug in a given shipment will be documented in the study files. The sponsor-investigator must be notified immediately of any discrepancies, damaged or unusable products that are received.

5.9.2 Storage

Dupilumab should be stored refrigerated at 36°F to 46°F (2°C to 8°C) in the original carton to protect from light. If necessary, pre-filled syringes may be kept at room temperature up to 77°F (25°C) for a maximum of 14 days. Dupilumab should not be stored above 77°F (25°C). After removal from the refrigerator, dupilumab must be used within 14 days or discarded. The syringe should not be exposed to heat or direct sunlight.

5.9.3 Dispensing of Study Drug

Regular study drug reconciliation will be performed to document drug assigned, drug dispensed, drug returns, and drug remaining. This reconciliation will be logged on tracked using the Vestigo electronic ledger system. Drug dispensation will occur at the first treatment visit.

5.9.4 Return or Destruction of Study Drug

At the completion of the study, there will be a final reconciliation of drug shipped, drug dispensed, drug returns, and drug remaining. This reconciliation will be logged on the drug reconciliation form, signed and dated. Any discrepancies noted will be documented and investigated, prior to return or destruction of unused study drug. Drug destroyed on site will be documented in the study files.

6 Study Procedures

6.1 Visit 1 (Week -2/Screening & Enrollment)

After the subject has provided written informed consent, the following information will be collected:

1. Informed consent
2. Inclusion and exclusion criteria
3. Medical history

The following procedures and assessments will be conducted:

1. PRNS score
2. Laboratory samples including; CBC with differential, AST, ALT, INR
3. Dispense pruritus scoring journal; review instructions

6.2 Visit 2 (Week 0+7 days Baseline)

The following information will be collected:

1. Inventory of existing medications and procedures

The following procedures and assessments will be conducted:

1. Vital signs including; height, weight, body temperature, blood pressure, pulse rate
2. Physical examination
3. Dispense study drug, 12 week supply of dupilumab
4. Instruct subject on self-injection of study drug
5. Observe subject injection technique
6. Review pruritus daily scoring journal; review instructions
7. PRNS score
8. VRS score
9. CLDQ questionnaire

6.3 Visit 3 (Week 6± 5 days)

The following information will be collected:

1. Inventory of existing medications and procedures

2. Adverse events

The following procedures and assessments will be conducted:

1. PNRS score; collect pruritus scoring journal
2. VRS score
3. Vital signs including; height, weight, body temperature, blood pressure, pulse rate
4. Physical examination
5. Laboratory samples including; CBC with differential, AST, ALT, INR
6. Dispense pruritus scoring journal; review instructions

6.4 Visit 4 (Week 12± 5 days)

The following information will be collected:

1. Inventory of existing medications and procedures
2. Adverse events

The following procedures and assessments will be conducted:

1. PNRS score; collect pruritus scoring journal
2. VRS score
3. Vital signs including; height, weight, body temperature, blood pressure, pulse rate
4. Physical examination
5. Laboratory samples including; CBC with differential, AST, ALT, INR
6. Dispense pruritus scoring journal; review instructions
7. Dispense study drug 6 week supply of dupilumab

6.5 Visit 5 (Week 18+2 days)

The following information will be collected:

1. Inventory of existing medications and procedures
2. Adverse events

The following procedures and assessments will be conducted:

1. PNRS score; review pruritus scoring journal
2. VRS score
3. CLDQ questionnaire
4. 5D itch score questionnaire
5. Vital signs including; height, weight, body temperature, blood pressure, pulse rate
6. Physical examination
7. Laboratory samples including; CBC with differential, AST, ALT, INR

6.6 Visit 6-Follow-up (Week 20±5 days)

The following information will be collected:

1. Inventory of existing medications and procedures
2. Adverse events

The following procedures and assessments will be conducted:

1. PNRS post-treatment score; collect pruritus scoring journal

TABLE OF EVENTS SUMMARY						
Week	Wk -2 Screening Enrollment	Wk 0 Baseline	Wk 6 ± 5 days	Wk 12 ± 5 days	Wk 18 ± 2 days	Wk 20 ± 5 days
Visit	1	2	3	4	5	6
Consent/Enroll	X					
Medical History	X	X	X	X	X	
Dispense Drug		X		X		
Dispense Pruritus Log	X		X	X		
Vital Signs	X	X	X	X	X	X
Physical Exam	X	X	X	X	X	X
PNRS	X	X	X	X	X	X
VRS		X		X	X	
5D Pruritus		X			X	
CLDQ		X			X	
CBC with diff	X		X	X	X	
AST/ALT	X		X	X	X	
PT/INR	X		X	X	X	
AE Event Screen		X	X	X	X	X

7 Statistical Plan

7.1 Sample Size Determination

No formal power analysis was performed as this is a pilot study; however, the open-label study design aids in the detection of therapeutic efficacy given the well-established natural history of chronic hepatic pruritus that at baseline has been characterized as persistent, severe, and not association with a natural history of spontaneous improvement.

7.2 Statistical Methods

Descriptive Statistics

Continuous variables will be summarized using the sample mean, median, standard deviation, interquartile range, and range. Categorical variables will be summarized using number and percentage of patients.

Handling of Missing Data

In the event of any unexpected missing data, this will be imputed using the last observation carried forward method.

Multiplicity

Since this is an exploratory pilot study, no adjustment for multiple testing will be undertaken.

Primary Hypothesis: For subjects with chronic hepatic pruritus, treatment with dupilumab will improve the PRNS after 1 weeks of treatment.

As previously described, the PRNS will be assessed on a daily basis for each patient. Separately for the 7 days prior to treatment (i.e. pre-treatment), the first 6 weeks of treatment (i.e. weeks 1 to 6), the second six weeks of treatment (i.e. weeks 7 to 12), the third six weeks of treatment (i.e. weeks 13 to 18), and the final two weeks of treatment (i.e. weeks 19 and 20), the mean of these daily PRNS measures will be calculated for each patient, resulting in a pre-treatment, week 6, week 12, week 18, and week 20 mean PRNS measurement for each patient. We will summarize the percentage change in PRNS values from pre-treatment to week 6, week 12, week 18, and week 20 using the aforementioned descriptive statistics. Additionally, we will estimate the proportion of patients whose mean PRNS value improves by 3 or more point, and by 4 or more points, from pre-treatment to each of the week 6, week 12, week 18, and week 20 time periods. Comparisons of mean PRNS between the pre-treatment time period and each of the week 6, week 12, week 18, and week 20 time periods will be made using a paired Wilcoxon signed rank test.

For secondary endpoints (VRS, 5D pruritus score, and CLDQ), these will be compared between the pre-treatment and follow-up time points using a paired Wilcoxon signed rank test. Although focus will be more on descriptive summaries rather than statistical significance due to the pilot nature of the study, p-values less than 0.05 will be considered as statistically significant.

Interim Analysis

There will not be any interim analysis given the low risk profile of the study formulation and the pilot nature of the study.

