1.5 Dose Rationale

The dose regimen of subcutaneous (SC) dupilumab selected for this study is 300 mg every 2 weeks for 18 weeks. All patients will get an initial loading dose of 600 mg (given as two 300 mg injections) at week 0. The administration of the loading dose of dupilumab will allow systemic concentrations to reach steady-state faster and reduce the time to onset of clinical effect. The dose of dupilumab for this study was based on the efficacy and safety results from multiple clinical trials that have led to the FDA approval of dupilumab at an initial dose of 600 mg then 300 mg every 2 weeks, for 18 weeks, for the treatment of atopic dermatitis.

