3.4 Primary Study Endpoints

The primary endpoint of the study will be the mean percent change in the Peak Pruritus Numerical Rating Score (PNRS) before and after 20 weeks of treatment with dupilumab. Pruritus severity is measured using the peak NRS assessed as a single, self-completed item that assesses the intensity of peak (worst) pruritus during the past 24 hours using the query: "On a scale of 0 to 10, with 0 being 'no itch' and 10 being 'worst itch imaginable', how would you rate your itch at the worst moment during the previous 24 hours?". The baseline and treatment mean peak PNRS will be the average of the daily score for 7 days before treatment and then after the first treatment dose self-assessed by patients daily and then averaged for 7 days.

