3.5 Secondary Study Endpoints

The other secondary endpoints regarding pruritus will be assessed at baseline and as follows:

1. Percentage of patients with an improvement in weekly average PNRS 3 from baseline. This will be assessed at week 6,12,18
2. Percentage of patients with an improvement in weekly average PNRS 4 from baseline. This will be assessed at week 6,12,18
3. Mean change in the verbal rating scale (VRS) of pruritus as measured 0=none; 1= mild; 2=moderate; and 3=severe/intense. This will be assessed at week 6,12,18
4. Mean change of 5D pruritus score. This is a multidimensional questionnaire designed to assess the degree, duration, direction, disability and distribution of pruritus longitudinally with scoring ranging from 5=no pruritus/well-controlled to 25=severe pruritus/poorly controlled. This will be assessed at baseline and at week 18.
5. Chronic Liver Disease Questionnaire (CLDQ). This is a validated quality life instrument for patients with chronic liver disease evaluating systemic symptoms, fatigue, physical activity, emotional function, and worry using a 7 point scale with 1=all of the time; 2=most of the time; 3=a good bit of the time; 4=some of the time; 5=a little of the time; 6=hardly any of the time; and 7=none of the time. This will be assessed at baseline and week 18.

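### The 3- and 4-point PNRS responder endpoints are defined on a weekly average in section 3.5 but calculated on six-week averages, under the same week labels, in section 7.2

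*Combined protocol and SAP*

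**What the plan says.** Section 3.5 lists two responder endpoints: "Percentage of patients with an improvement in weekly average PNRS 3 from baseline. This will be assessed at week 6,12,18" and "Percentage of patients with an improvement in weekly average PNRS 4 from baseline. This will be assessed at week 6,12,18". A comparison sign before the 3 and the 4 has probably been lost in conversion. That does not affect the averaging window, which is plainly one week.

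Section 3.4 describes on-treatment scores as "self-assessed by patients daily and then averaged for 7 days". It does not say which on-treatment week is meant, so it supports a 7-day window without fixing one.

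Section 7.2 takes the mean of the daily scores over the 7 days before treatment, then over "the first 6 weeks of treatment (i.e. weeks 1 to 6), the second six weeks of treatment (i.e. weeks 7 to 12"), weeks 13 to 18, and weeks 19 and 20, "resulting in a pre-treatment, week 6, week 12, week 18, and week 20 mean PRNS measurement for each patient". From these values "we will estimate the proportion of patients whose mean PRNS value improves by 3 or more point, and by 4 or more points". The same values feed the percentage-change summaries and the signed-rank tests.

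**The concern.** A mean over weeks 1 to 6 is not a weekly average at week 6. It includes the first days after the first dose and is compared with a 7-day baseline. Average itch over a period is a legitimate quantity, but it answers a different question from the patient's state at a visit week.

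The direction of the difference depends on the course of itch. If improvement is gradual, the block mean dilutes response, mainly at week 6. If response wanes, the block mean overstates it at weeks 12 and 18. If improvement is early and stable, the two nearly agree.

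With 12 subjects, each reclassified patient moves a responder rate by 1/12 = 8.3 percentage points. The study is open-label, and section 13 says its data could support a larger trial. Two written definitions leave room to choose between them after the diaries have been seen.

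**Working it through.** **1. The definitions side by side**

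| Label | Section 3.5 | Section 7.2 |
|---|---|---|
| Baseline | window not stated | 7 days before treatment |
| Week 6 | weekly average (7 scores) | weeks 1–6 (42 scores) |
| Week 12 | weekly average (7 scores) | weeks 7–12 (42 scores) |
| Week 18 | weekly average (7 scores) | weeks 13–18 (42 scores) |
| Week 20 | not listed | weeks 19–20 (14 scores) |

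No section says that the six-week mean replaces the weekly average or that both will be reported. The conflict is established by this comparison alone. Its size has to be illustrated, because the documents give no effect size, SD, responder rate or onset time for itch. Section 1.5 says only that the loading dose should "reduce the time to onset of clinical effect". Every input below is therefore an assumption.

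**2. Two patients, by hand**

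- *Gradual improver.* Weekly reductions in weeks 1–6 are 0.67, 1.33, 2.00, 2.67, 3.33 and 4.00. The weekly average at week 6 shows 4.00, a responder on both cut-offs. The block mean is 14/6 = 2.33, a non-responder on both.
- *Waning response.* The reduction is 4 points in weeks 1–3 and 2 points in weeks 4–6. The weekly average shows 2.00. The block mean is (3×4 + 3×2)/6 = 3.00, so the 3-point status reverses the other way.

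**3. Mean reduction, exponential onset**

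Let the reduction at t weeks be 4 × (1 − exp(−t/τ)). I compared days 36–42 with 1–42, 78–84 with 43–84, and 120–126 with 85–126. Worked example for τ = 2 at week 6:

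- Weekly: 4 × [1 − 2 × (e^−2.5 − e^−3)] = 4 × [1 − 2 × (0.0821 − 0.0498)] = 3.74
- Block: 4 × [1 − (2/6) × (1 − e^−3)] = 4 × [1 − 0.317] = 2.73
- Shortfall: 1 − 2.73/3.74 = 27%

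| τ (weeks) | Weekly, week 6 | Block, week 6 | Shortfall* |
|---|---|---|---|
| 0 (immediate) | 4.00 | 4.00 | 0% |
| 0.5 | 4.00 | 3.67 | 7–8% |
| 1 | 3.98 | 3.34 | 15–16% |
| 2 | 3.74 | 2.73 | 26–27% |
| 4 | 2.99 | 1.93 | 35% |
| 6 | 2.40 | 1.47 | 38–39% |
| linear rise to week 6 | 3.67 | 2.00 | 45% |

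*Ranges come from timing each score at mid-day or at the end of the day.

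Under the exponential curves the shortfall is 0–10% at week 12 and 0–3% at week 18.

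**4. Four-point responders, weekly vs block**

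I simulated 400,000 subjects. Baseline was N(7, 1.5) limited to 4–10. Maximum reduction was N(4, 2) capped at baseline. Error SD was 0.5 for both means.

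| τ (weeks) | Week 6 | About, of 12 | Week 12 | Week 18 |
|---|---|---|---|---|
| 0 | 49% vs 49% | 6 vs 6 | 49% vs 49% | 49% vs 49% |
| 0.5 | 49% vs 41–42% | 6 vs 5 | 49% vs 49% | 49% vs 49% |
| 1 | 49% vs 33% | 6 vs 4 | 49% vs 49% | 49% vs 49% |
| 2 | 43% vs 16% | 5 vs 2 | 49% vs 48% | 49% vs 49% |
| 4 | 23% vs 1% | 3 vs 0 | 44% vs 38% | 48% vs 47% |
| 6 | 8% vs 0% | 1 vs 0 | 35% vs 25% | 44% vs 41% |

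Three-point responders at week 6 show the same pattern: 68% vs 57% at τ = 1 and 65% vs 41% at τ = 2.

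**5. Waning**

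Assume full effect to week 6, then a linear loss to a fraction p by week 18. The fraction remaining at t weeks is 1 − (1 − p)(t − 6)/12. Each mean equals the value at the middle of its window.

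| p | Week | Block | Weekly | Ratio |
|---|---|---|---|---|
| 0.6 | 12 | 0.900 | 0.817 | 1.10 |
| 0.6 | 18 | 0.700 | 0.617 | 1.14 |
| 0.5 | 12 | 0.875 | 0.771 | 1.14 |
| 0.5 | 18 | 0.625 | 0.521 | 1.20 |

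The block mean overstates the reduction by 10–14% at week 12 and 14–20% at week 18.

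**6. Noise of the shorter window**

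With an assumed day-to-day SD of 1.5 and independent days, the SD of the mean is 1.5/√7 = 0.57 for 7 days and 1.5/√42 = 0.23 for 42 days. With autocorrelation 0.5 these become 0.88 and 0.39.

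**The case against.** The strongest reply is that section 7.2 is explicit and can be carried out as written. It gives windows, labels, cut-offs and a test, whereas 3.5 never says which seven days count. An analyst working only from 7.2 has one calculation to do. On this view the defect is a mismatch of labels in secondary endpoints of an unpowered 12-subject pilot that puts description ahead of significance. The block mean is also more precise and less exposed to missed diary days. Rewriting 3.5 to describe period means, with honest labels, would remove the contradiction too.

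Much of this is fair. The large differences are confined to week 6. At week 18, the time point of the primary endpoint in the Study Summary, the modelled onset curves differ by about 3 percentage points at most, or roughly 0.4 of a patient in 12. All sizes are assumed, and nothing in the documents points to waning.

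It does not remove the point. An analyst who follows 7.2 still does not report the endpoint in 3.5, and these proportions are exactly the descriptive summaries on which the study relies. Relabelling would cure the inconsistency, but the 7-day baseline in 7.2, the 7-day averaging in 3.4 and the weekly average in 3.5 all favour the weekly window. Precision is a reason to keep the block means as a supportive summary, not to let them stand for a single week.

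**Conclusion.** The concern holds. Sections 3.5 and 7.2 define the responder endpoints on different averaging windows under the same week labels, and nothing reconciles them. That conclusion rests on the text alone and needs no assumption.

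The numerical consequence does depend on assumptions about baseline, effect, variability and onset. At week 6 it ranges from nothing to the loss of nearly all four-point responders. On the modelled onset curves it is modest at week 12 and small at week 18. The block means also feed the percentage changes and the signed-rank tests, so the mismatch reaches beyond the responder rates. It should be corrected before analysis, but it does not threaten the conduct of the study.

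**What to change.** In section 7.2:

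- Define the week 6, 12 and 18 PNRS as the mean of the daily journal scores on days 36–42, 78–84 and 120–126 after the first dose. Use fixed study days, because the week 6 and week 12 visits may move by up to 5 days.
- Use these values for the 3- and 4-point responder rates, the percentage changes and the signed-rank tests.
- State how many of the 7 scores a valid mean needs (for example 4), and how last observation carried forward applies below that number.
- For consistency, use a 7-day window at week 20 as well, although 3.5 does not list that week. Take the last 7 scores before visit 6, because the journal is collected at that visit and its date can move.
- Keep the six-week means as a supportive summary, labelled as average itch over weeks 1–6, 7–12 and 13–18.

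The cost is SAP wording only. The daily scores already exist: at the week 6 and week 12 visits the old journal is collected and a new one issued ("Dispense pruritus scoring journal; review instructions"), and the journal reviewed at week 18 stays with the patient until week 20. The price is a noisier value (SD 0.57–0.88 against 0.23–0.39 under the assumptions above) that is more sensitive to missed diary days and to carrying the last observation forward.
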